2.4.4.2 Analyses of secondary efficacy endpoints

2.4.4.2.1 Absolute/percent change from baseline for continuous endpoints

The key secondary endpoint, percent change from baseline in pre-bronchodilator FEV1 at Week 12, will be analyzed in the same way as for change from baseline in FEV1 at Week 12, with the only difference that percent changes, instead of absolute changes, from baseline in FEV1 up to Week 12 will be included as the response variables. MMRM model including measurements up to Week 52 will also be used to derive LS mean change at all time-points. Differences in LS means, the corresponding 95% CI and the p-value will be provided for comparisons of each dupilumab dose against its matching placebo along with descriptive statistics.

Change from baseline in ACQ-5 and AQLQ at Week 24 will be analyzed using MMRM including change from baseline up to Week 24 as response variables, regardless if the patient is on treatment or not when the endpoint is measured. The model will include treatment, age, region (pooled country), baseline eosinophil strata, baseline ICS dose level, visit, treatment by-visit interaction, baseline endpoint value, and baseline-by-visit interaction as covariates. MMRM model including measurements up to Week 52 will also be used to derive LS mean change at all time-points. Differences in LS means, the corresponding 95% CI and the p-value will be provided for comparisons of each dupilumab dose against its matching placebo along with descriptive statistics.

Change from baseline in other continuous endpoint at all time-points will be analyzed using MMRM model including measurements up to Week 52. The model will include change from baseline in the endpoint values from Week 2 to Week 52 as response variables, regardless if the patient is on treatment or not when the endpoint is measured, and treatment, age, sex, baseline height, region (pooled country), baseline eosinophil strata, baseline ICS dose level, visit, treatment by-visit interaction, baseline endpoint value and baseline-by-visit interaction as covariates. Sex and baseline height will be included as covariates only in the models for spirometry parameters. Differences in LS means, the corresponding 95% CI and the p-value will be provided for comparisons of each dupilumab dose against its matching placebo along with descriptive statistics.

For post-bronchodilator FEV1, the rate of change in FEV1 (termed as FEV1 slope) will be compared between each dupilumab dose against its matching placebo. Change from baseline in post-bronchodilator FEV1 after Week 4 and after Week 8 will be analyzed correspondingly using linear mixed-effects model with treatment, age, sex, height, region (pooled country), baseline eosinophil strata, baseline ICS dose level, time since randomization, and treatment-by-time interaction and baseline post-bronchodilator FEV1 as covariates.

In addition to the MMRM analyses for change from baseline in ACQ-5, ACQ-7 and AQLQ total score a responder analysis will also be performed for these endpoints at Week 12, 24, 36 and 52. For ACQ-5 score, a logistic regression model will be used to compare percentage of patients who reached MCID (responders) in each dupilumab dose group against its matching placebo at the time points aforementioned correspondingly. Patients with change from baseline in ACQ-5 ≤ -0.5 will be considered as responders. Patients with change from baseline in ACQ-5 > -0.5 or with missing value will be considered as non-responders. The model will include treatment, age, region (pooled country), baseline eosinophil strata, baseline ICS dose level, and baseline ACQ-5 score as covariates. Odds ratio of being a responder comparing each dupilumab dose group to its matching placebo group will be provided along with the corresponding 95% CI and p-value. Descriptive statistics including number and percentage of responders will also be provided. Responder analysis for ACQ-7 and AQLQ global score will be performed in the same way. For ACQ-7, a patient is considered as a responder if change from baseline in ACQ-7 score ≤ -0.5 , or as a non-responder if change from baseline in ACQ-7 score > -0.5 or missing. For AQLQ global score, a patient is considered as a responder if change from baseline in AQLQ global score ≥ 0.5 , or as a non-responder if change from baseline < 0.5 or missing. ACQ-7 score will also be analyzed in adolescent patient population separately.

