Archival serum l	x																																																					
EQ-5D-5L	x																																																					
HADS m	x																																																					
SNOT-22 n	x																																																					
RQLQ(S) +12 o	x																																																					
Vaccine IgG p	x																																																					

- a** Patients who permanently discontinue treatment early will continue the remaining visits per protocol schedule with a +/-5 day window until end of study. At the time of permanent treatment discontinuation, patients will perform early treatment discontinuation (ETD) visit with all the assessments defined for Visit 18 (EOT). Visit 19 (Week 56) and Visit 20 (Week 60) will not be performed.
- b** Forced expiratory volume (FEV1), PEF, Forced vital capacity (FVC), Forced expiratory flow between 25% to 75% of vital capacity (FEF25%-75%) at all visits; pulmonary function tests should be performed in the morning if possible, but if it could only be done at a different time of the day, the spirometry should be done at approximately the same time of the day at each visit throughout the study. Spirometry will be performed after a wash out period of bronchodilators according to their action duration, for example, withholding the last dose of salbutamol/albuterol or levosalbutamol/levalbuterol for at least 6 hours and withholding the last dose of LABA for at least 12 hours (ultra-long acting LABA like vilanterol should be withheld for at least 24 hours) and withholding the last dose of Long-Acting Muscarinic Antagonist (LAMA) for at least 24 hrs. This will be verified before performing the measurements.
- c** Electronic diary/PEF meter is used for daily recording of salbutamol/albuterol or levosalbutamol/levalbuterol use, asthma controller drug use, oral steroid requirements, nocturnal awakenings due to asthma symptoms, morning and evening asthma symptom NRS scores and AM and PM PEF. This device is dispensed at Visit 1 and information is downloaded from this device on the other indicated days.

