  - Use of daily puffs of rescue medication
- Change from baseline in Health care resource utilization at Weeks 12, 24, 36, and 52.
- Change from baseline in PROs at Week 12, 24, 36, and 52:

- Asthma Quality Of Life Questionnaire with Standardized Activities (AQLQ (S)) Self-Administered ( $\geq 12$  years)
- European Quality of Life Working Group Health Status Measure 5 Dimensions, 5 Levels (EQ-5D-5L)
- Hospital Anxiety and Depression Scale (HADS)
- 22-item Sino Nasal Outcome Test (SNOT-22) in those patients with comorbid bilateral nasal polyposis and/or chronic rhinosinusitis
- Standardized Rhinoconjunctivitis Quality Of Life Questionnaire, ages 12+ (RQLQ(S)+12) in those patients with comorbid allergic rhinitis

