- Call IVRS/IWRS to register the EOT date (only applicable for EOT visit)

At Visit 18 (EOT visit), for patients who will not continue with the open label extension, the controller medication regimen and dose used during the randomized period could be adjusted based on medical judgment of the patients' asthma control status.

Patients who permanently discontinue the study treatment will perform early treatment discontinuation visit (ETD) at the time of permanent treatment discontinuation as well as EOT visit (visit 18) at planned Week 52. See section 1.3 for assessments to be performed at ETD and EOT visits and Section 10.3.4 for additional details.

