### **10.3.4 Handling of patients after permanent treatment discontinuation**

Patients will be followed-up according to the study procedures as specified in this protocol up to the scheduled date of study completion, or up to recovery or stabilization of any AE to be followed-up as specified in this protocol, whichever comes last.

Patients who permanently discontinue the study medication will be asked and encouraged to return to the clinic for study visits and participate in assessments according to the visit schedule until the end of the study with a +/-5 day window (See Section 1.3). Under exceptional circumstances when a patient cannot come to the site for the scheduled visit, a phone contact can be made after sponsor approval is given. During the phone contact, at least information about AEs, concomitant medication and asthma exacerbation events should be collected.

Patients who discontinue early from treatment may be asked to return to the clinic to have additional ADA samples collected for analysis based on the overall assessment of antibody titers and/or clinical presentation at the time of discontinuation.

All cases of permanent treatment discontinuation should be recorded by the Investigator in the appropriate pages of the CRF when considered as confirmed.

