#### **11.4.5 Analyses of Patient Reported Outcomes (Health-related Quality of Life/health economics variables)**

Change from baseline in the following variables: global measure of AQLQ(S) and the four domains, the quantitative variables of EQ-5D-5L (single index utility), the anxiety and depression scores of HADS will be analyzed with an MMRM approach described previously for the continuous efficacy variables. Descriptive statistics including number of patients, mean, standard error and LS means will be provided. In addition, difference in LS means, the corresponding 95% CI's and the p-values will be provided for comparison between dupilumab and placebo.

SNOT-22 (only for those patients with bilateral nasal polyposis and/or chronic rhinosinusitis) and RQLQ(S)+12 (only for those patients with comorbid allergic rhinitis) will be analyzed using the similar approach.

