2.1.4 Safety endpoints

The safety analysis will be based on the reported adverse events and other safety information, such as clinical laboratory data, vital signs, ECG and physical examination.

Observation period

The observation period will be divided into 4 epochs:

- The **screening** epoch is defined as the time from the signed informed consent date up to the time prior to first administration of the IMP.
- The **treatment** epoch is defined as the time from the first administration of the IMP to the last administration of the IMP + 14 days or until rollover to the LTS12551 study.
- The **residual treatment** epoch is defined as the time from the last administration of the IMP +15 days to the last administration of the IMP + 98 days or until rollover to the LTS12551 study.
- The treatment-emergent adverse event period will include both **treatment** and **residual treatment** epochs.
- The **posttreatment** epoch is defined as the period of time starting the day after the end of the treatment-emergent adverse event period up to the end of the study (defined as last protocol planned visit or the resolution/stabilization of all serious adverse events and adverse events with pre-specified monitoring).

The on-study observation period is defined as the time from start of treatment until the end of the study (defined as last protocol planned visit or lost to follow-up or the resolution/stabilization of all serious adverse events and adverse events with pre-specified monitoring).

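### Four patient-reported outcomes are not scheduled after the early discontinuation visit, so for patients who stop treatment their MMRM estimates to Week 52 rest on missing-at-random

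*SAP*

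**What the plan says.** **Endpoints.** Protocol 9.2.1 lists "Change from baseline in PROs at Week 12, 24, 36, and 52" as secondary endpoints: AQLQ(S), EQ-5D-5L, HADS, and, in the relevant comorbidity subsets, SNOT-22 and RQLQ(S)+12. SAP 2.1.3.2.2 repeats the list. The effect on patient-reported outcomes is a stated secondary objective.

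**Analysis.** Protocol 11.4.5 says the quality-of-life and HADS scores "will be analyzed with an MMRM approach described previously for the continuous efficacy variables", with a similar approach for SNOT-22 and RQLQ(S)+12. SAP 2.4.4.2.1 models the other continuous endpoints by MMRM from Week 2 to Week 52, with the changes entered "as response variables, regardless if the patient is on treatment or not when the endpoint is measured, and treatment" heading the covariate list. AQLQ is also analysed on or off treatment, to Week 24 for the tested comparison and to Week 52 for all time points.

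**Collection after stopping treatment.** Protocol 1.3, footnote a, states that "Patients who permanently discontinue treatment early will continue the remaining visits per protocol schedule with a +/-5 day window until end of study". At the moment of stopping there is also an ETD visit with the Visit 18 assessments. In the body of that chart, EQ-5D-5L, HADS, SNOT-22 and RQLQ(S)+12 carry a single mark each, at ETD. AQLQ(S) is marked at ETD and again at Weeks 12, 24, 36, 52 and 64.

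**The concern.** The analysis rule treats the patient-reported outcomes alike, but the collection schedule does not. A patient who stops treatment goes on supplying AQLQ(S) at each planned week still to come. The other four instruments yield one reading at ETD and nothing scheduled afterwards.

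For those four, missingness after ETD is triggered by stopping drug, which is where missing-at-random is least secure. The MMRM will in effect continue the patient's course as though treatment had not stopped. The AQLQ estimate includes the off-drug course wherever patients attend. Two kinds of effect would then sit next to each other in the report under the same kind of data rule. If benefit fades off drug, the four will look better than a measured follow-up would show. The SAP specifies control-based imputation and tipping-point analyses only for the two primary endpoints (2.4.4.1.1 and 2.4.4.1.2), so nothing tests the assumption here.

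**Working it through.** **1. Which schedule governs.** Protocol 10.3.4 asks discontinued patients to "participate in assessments according to the visit schedule until the end of the study with a +/-5 day window" and refers to Section 1.3. The closing paragraph of Protocol 10.1.11 is explicit about the ETD and Week 52 visits: "See section 1.3 for assessments to be performed at ETD and EOT visits". So chart 1.3 decides.

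**2. Scheduled assessments after ETD in chart 1.3.**

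| Instrument | Marks after ETD |
|---|---|
| AQLQ(S) | 5 (Weeks 12, 24, 36, 52, 64) |
| EQ-5D-5L | 0 |
| HADS | 0 |
| SNOT-22 | 0 |
| RQLQ(S)+12 | 0 |

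Spirometry and ACQ-7 also keep later marks. So do drug concentration and anti-drug antibodies, which stand in the same block of the table as the four questionnaires. The blank cells therefore look intended. Chart 1.2, for patients who complete treatment, marks all five instruments at Weeks 0, 12, 24, 36 and 52. The schedules part only after discontinuation.

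**3. What the model can receive.** SAP Table 9 gives all five instruments the same windows: days 1-126, 127-210, 211-308 and 309-406 for Weeks 12, 24, 36 and 52. For the four, a patient who stops contributes values up to ETD, and the ETD value goes into whichever window contains it. Later windows have nothing scheduled.

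**4. Possible size.** Let Δ be the on-drug difference from placebo, d the share stopped in each arm by the time point, and r the fraction of benefit kept off drug. Suppose values before and at ETD carry no information about the later course.

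- Difference including the off-drug course: Δ × (1 − d(1 − r))
- Relative overstatement if Δ is reported: 1/(1 − d(1 − r)) − 1

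| d (assumed) | r = 0 | r = 0.5 |
|---|---|---|
| 0.05 | 1/0.95 − 1 = 5.3% | 1/0.975 − 1 = 2.6% |
| 0.10 | 1/0.90 − 1 = 11.1% | 1/0.95 − 1 = 5.3% |
| 0.15 | 1/0.85 − 1 = 17.6% | 1/0.925 − 1 = 8.1% |

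The documents give no discontinuation rate, so both d and r are assumptions. At Week 24 fewer patients will have stopped than at Week 52, and the figure shrinks accordingly.

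**The case against.** The strongest reply is that the two documents do not contradict each other. The SAP sentence is a data-inclusion rule: a value counts if it is measured, whatever the treatment status. It does not promise that every instrument is measured after discontinuation. A shorter schedule that keeps the formally tested measures (spirometry, ACQ-5, AQLQ) is a defensible way to limit burden. That stands, and it makes this a matter of improvement and disclosure rather than error.

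Three stronger readings are tempting, and the documents do not support them.

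- *No off-treatment data exist for these four.* The ETD value is collected and can enter a Table 9 window. The SAP's treatment epoch (2.1.4) is "the time from the first administration of the IMP to the last administration of the IMP + 14 days", so an ETD visit later than that gives an off-treatment value. What is absent is scheduled follow-up after ETD.
- *The SAP presents these four as treatment-policy effects.* It uses that language only for the two primary endpoints.
- *The model fills the gap purely from patients still on drug.* An MMRM also conditions on the patient's own earlier values, including ETD. Worsening already visible by then carries forward.

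A further point is that the visit lists in Protocol 10.1.8 and 10.1.11 name all five questionnaires at Weeks 12, 24, 36 and 52. Those lists are general. For discontinued patients the text points to Section 1.3, so they do not close the gap.

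Finally, control-based imputation may seem disproportionate when the SAP does not specify it for AQLQ or ACQ-5. Those two have scheduled values after ETD and so lean less on missing-at-random.

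**Conclusion.** The point holds as a cheap improvement. For EQ-5D-5L, HADS, SNOT-22 and RQLQ(S)+12, every scheduled value after ETD is missing by design in patients who stop treatment. The MMRM estimates to Week 52 then depend on missing-at-random and lie closer to an on-treatment effect than the AQLQ estimate does. The overstatement is at most about 5%, 11% and 18% for assumed d of 0.05, 0.10 and 0.15. That ceiling needs nil off-drug benefit, equal discontinuation in the arms and no information from earlier values. Retained benefit, or information in the ETD reading, makes it smaller.

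A reader might infer that a confirmatory claim is at risk. It is not: none of the four is in the Table 6 hierarchy, and the tested patient-reported endpoints, AQLQ and ACQ-5, continue to be collected after ETD. What is affected is the reading of a stated secondary objective.

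**What to change.** **Preferred.** In chart 1.3, mark EQ-5D-5L, HADS, SNOT-22 and RQLQ(S)+12 at Weeks 12, 24, 36 and 52, alongside AQLQ(S). No visit is added. The cost is a flow chart change and a few more minutes of questionnaires for discontinued patients.

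**Check at the same time.** The e-diary/PEF row of chart 1.3 is also marked at ETD only. It feeds the morning and evening PEF, symptom-score, nocturnal-awakening and reliever-use endpoints, which fall under the same SAP sentence.

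**If collection can no longer change.** State in SAP 2.4.4.2.1 that these endpoints have scheduled data only up to and including ETD and are analysed under missing-at-random. Add one control-based sensitivity analysis, adapting the method already set out for FEV1 in 2.4.4.1.2. Do not label the endpoints on-treatment, because ETD can fall later than 14 days after the last dose and the SAP rule does not exclude such values. The cost is a short SAP edit before database lock and one extra analysis.

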## 10 STUDY PROCEDURES

### 10.1 VISIT SCHEDULE

The clinical trial consists of three periods, using an add-on therapy approach to inhaled corticosteroid in combination with one or two other controller medications:

- Screening Period (4±1 weeks; Visit 1)
- Randomized Treatment Period ( 52 weeks; Visits 2-18)
- Post-treatment Period (12 weeks; Visits 19-21)

The study visits occur on the planned dates (relative to the first injection), as scheduled. The visit schedule should be adhered to within the ± 3 day visit window.

All the study visits should be scheduled in the morning, to have the spirometry performed and the patient should be fasting for serum chemistry tests. However, if the visit can only be done at a different time of the day and the patient is not fasting, then he/she should be advised to have a light meal and the site should document that serum chemistry was not obtained under fasting conditions. For spirometry, it should be performed at approximately the same time of the day at each visit throughout the study.

Patients who permanently discontinue the study medication will be asked and encouraged to return to the clinic for study visits and participate in assessments according to the visit schedule until the end of the study with a +/-5 day window (See Section 1.3). Under exceptional circumstances when a patient cannot come to the site for the scheduled visit, a phone contact can be made after sponsor approval is given. During the phone contact, at least information about AEs, concomitant medication and asthma exacerbation events should be collected.

Patients who discontinue early from treatment or patients who choose not to participate in the OLE study may be asked to return to the clinic to have additional ADA samples collected for analysis based on the overall assessment of antibody titers and/or clinical presentation at the time of discontinuation or at the time of last study visit.

Reminder: sexually active female patients of reproductive potential are required to practice an effective contraception throughout the participation in the study including a 12-week period after last IMP dose. Sites should counsel these patients, with special attention towards adolescent patients regarding the importance of practicing responsible and effective contraception throughout the participation in the study including a 12-week period after last IMP dose.

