1.3 DETERMINATION OF SAMPLE SIZE

The sample size was calculated on a comparison between dupilumab 300 mg q2w versus placebo with regard to the 2 primary endpoints: annualized rate of severe asthma exacerbations during the 52-week treatment period, and absolute change from baseline in FEV1(L) at Week 12. Assuming the number of severe asthma exacerbations follows a negative binomial distribution with a dispersion parameter of 2, a placebo annualized rate of exacerbations being 0.6, a randomization ratio of 2:2:1:1, with 1638 randomized patients (546 for each dupilumab dose and 273 for each matching placebo group), the study will have 99% power to detect a 55% relative risk reduction (ie, annualized rate of 0.27 for the dupilumab group) in the annualized rate of severe asthma exacerbations at the 2-tailed significance level of $\alpha=0.05$. Assuming 42% patients with a baseline blood eosinophil count ≥ 0.3 Giga/L, approximately 690 patients (230 for dupilumab 300mg q2w and 115 for the matching placebo) will provide 91% power to detect a 55% relative risk reduction for this subgroup. Assuming a common standard deviation of 0.5 L, 1638 patients (546 for each dupilumab dose and 273 for each matching placebo group) will provide 98% power to detect a treatment difference of 0.15 L in the change of FEV1 from baseline at Week 12 for the overall population, and 690 patients (230 for dupilumab 300mg q2w and 115 for the matching placebo) will provide 88% power to detect a treatment difference of 0.18 L for patients with a baseline blood eosinophil count ≥ 0.3 Giga/L. The overall study recruitment will continue until at least 1638 patients in total and 690 patients with blood eosinophils ≥ 0.3 Giga/L are randomized. The recruitment for patients on treatment of medium dose of ICS will stop when approximately 819 patients in this category have been randomized into the study. In addition, approximately 84 adolescent patients will be randomized.

In addition to the originally planned sample size of 1638 patients, approximately 220 patients will be randomized in order to have additional patients treated with the drug product manufactured using the intended commercial process.

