2.3.1.1 Intent-to-treat population

The intent-to-treat population is the randomized population analyzed according to the treatment group allocated by randomization.

Patients will be analyzed in the treatment group to which they are randomized.

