2.5.3 Missing data

For categorical variables, patients with missing data are not included in calculations of percentages unless otherwise specified. When relevant, the number of patients with missing data is presented.

Handling of missing answer to the 7th question in ACQ-7

If the score is missing from the site report, the FEV1 % predicted value from spirometry test will be used to derive the 7th score. Only the spirometry performed on the same day when ACQ-7 is evaluated will be used. And if there are multiple FEV1% predicted values available on the same day, the lowest one will be used to score the 7th item. If the score of the 7th question is still missing but the questionnaire is complete at the prior visit, the missing score for the 7th question will be imputed as: (score of the 7th question at the prior visit) \times (sum of scores of the first six questions at the current visit) / (sum of scores of the first six questions at the prior visit). If the questionnaire from the prior visit is not complete either or if the ACQ-7 score at the prior visit is 0, which makes it infeasible to implement the algorithm, the missing score will be imputed as the average of the other six questions at the current visit. If scores of the first six questions are missing, then the ACQ-7 score for the current visit will be missing.

Handling of computation of treatment duration if investigational medicinal product end of treatment date is missing

For the calculation of the treatment duration, the date of the last dose of IMP is equal to the date of last administration reported on the Investigational Product Administration report form page. If this date is missing, the exposure duration should be left as missing.

The last dose injection should be clearly identified in the case report form and should not be approximated by the last returned package date.

Handling of medication missing/partial dates

No imputation of medication start/end dates or times will be performed. If a medication date or time is missing or partially missing and it cannot be determined whether it was taken prior or concomitantly, it will be considered a prior and concomitant medication.

Handling of adverse events with missing or partial date/time of onset

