Visit 18 (Week 52)	365	351-378	309-406	351-378		351-406	309-406	>308	
Visit 19 (Week 56)	393	379-406		379-406					
Visit 20 (Week 60)	421	407-434		407-434					
Visit 21 (Week 64)	449	>434	>406	>434		>406	>406		

1-: up to 1st dose date/time; 1+: after 1st dose date/time;

For the efficacy assessment, the reference date for the derivation of relative days of events or findings will be the randomization day. If a patient receives IMP prior to the randomization by mistake, the reference date of efficacy assessment will be the date of the first IMP administration for that patient. For the primary analyses, all available values of scheduled measurements will be assigned to the appropriate visit window according to Table 9. In the event of multiple measurements of the same test in the same window, the one closest to the targeted visit date will be used for the by-visit summary. If they are at the same distance to the target day, the latest one will be used. For the on-treatment sensitivity analyses, only scheduled measurements collected during the treatment epoch will be assigned to a time window.

Table 9 – Time window for efficacy variables

Visit	Target Day	Time windows for		
		Pre-bronchodilator Spirometry, ACQ-5, ACQ-7	Post-bronchodilator spirometry, reversibility	AQLQ(S), EQ-5D-5L, HADS, SNOT-22, RQLQ(S)+12
Visit 1 (Week -4±1)	-28±7	<-14		
Visit 2 (Week 0)	1	-14-1 ¹	1 ¹	1 ¹
Visit 3 (Week 2)	15	1 ⁺ -21	1 ⁺ -21	
Visit 4 (Week 4)	29	22-35	22-42	
Visit 5 (Week 6)	43	36-49		
Visit 6 (Week 8)	57	50-63	43-70	
Visit 7 (Week 10)	71	64-77		
Visit 8 (Week 12)	85	78-98	71-126	1-126
Visit 9 (Week 16)	113	99-126		
Visit 10 (Week 20)	141	127-154		
Visit 11 (Week 24)	169	155-182	127-210	127-210
Visit 12 (Week 28)	197	183-210		
Visit 13 (Week 32)	225	211-238		
Visit 14 (Week 36)	253	239-266	211-308	211-308
Visit 15 (Week 40)	281	267-294		
Visit 16 (Week 44)	309	295-322		
Visit 17 (Week 48)	337	323-350		
Visit 18 (Week 52)	365	351-378	309-406	309-406
Visit 19 (Week 56)	393	379-406		
Visit 20 (Week 60)	421	407-434		
Visit 21 (Week 64)	449	>434	>406	>406

1⁻: up to randomization and before 1st dose date/time; 1⁺: after randomization or 1st dose date/time

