4 DATABASE LOCK

The database lock is planned based on the time when approximately 1638 patients (originally planned sample size) complete Week 52 visit or discontinue from the study before Week 52. Analyses will be based on all data collected up to this database lock and will be considered as the final analyses in the CSR. Additional data between database lock and last patient completing last visit will be summarized in CSR addendum.

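### The Week 52 ACQ-5, ACQ-7 and AQLQ responder analyses count as failures about 220 of about 1858 ITT patients whose Week 52 visit has not happened at the planned lock

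*SAP*

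**What the plan says.** Four provisions of the SAP combine.

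- **Sample size (1.3).** Beyond the original 1638, "approximately 220 patients will be randomized in order to have additional patients treated with the drug product" made by the intended commercial process.
- **Population (2.3.1.1).** "The intent-to-treat population is the randomized population analyzed according to the treatment group allocated by randomization". Protocol 11.3.1 agrees. Neither document limits an efficacy analysis to the first 1638 patients or to those who could have reached Week 52.
- **Lock (4).** The database is locked "when approximately 1638 patients (originally planned sample size) complete Week 52 visit or discontinue from the study before Week 52". The final study report uses the data held at that point. Later data go to an addendum.
- **Responder rule (2.4.4.2.1).** ACQ-5, ACQ-7 and AQLQ responders are compared at Weeks 12, 24, 36 and 52 by logistic regression. For ACQ-5, "Patients with change from baseline in ACQ-5 > -0.5 or with missing value will be considered as non-responders". ACQ-7 and AQLQ have the equivalent rule.

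A general convention in SAP 2.5.3 points the other way: "For categorical variables, patients with missing data are not included in calculations of percentages unless otherwise specified". The responder section does specify otherwise, so the convention gives way to it.

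**The concern.** Scoring a missing value as failure is a reasonable, conservative choice when a patient drops out. It makes no sense for a patient who is still in the trial and has not yet reached the visit. That gap is administrative and says nothing about response.

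The Week 52 responder percentages, odds ratios, confidence intervals and p-values in the study report would therefore depend on when the lock falls. The Week 52 rates would also not be comparable with those at Weeks 12 and 24, so an artefact could look like a late loss of response.

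The other efficacy analyses do not share the problem. The exacerbation model uses a duration offset, the time-to-event endpoints are censored at Visit 18 or last contact (SAP 2.1.3.2.2.3), and the MMRM imputes no failures. Table 2 of the SAP records the change to the lock but no matching change to the responder rule.

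**Working it through.** **The plan's own figures.** The documents give no count of patients still in follow-up at lock and no power for the responder analyses. The sample-size figures they do give were recomputed from their stated inputs, using a Wald test on the log rate ratio with dispersion 2 and one year of follow-up, and a two-sample comparison of means with SD 0.5 L:

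| Comparison | Stated power | Recomputed |
|---|---|---|
| Exacerbations, 546 vs 273 | 99% | 99.9% |
| Exacerbations, 230 vs 115 | 91% | 91.8% |
| FEV1, 546 vs 273 | 98% | 98.2% |
| FEV1, 230 vs 115 | 88% | 88.3% |

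The planned arm sizes are therefore a sound base.

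**Share not yet due at lock.**
- Total randomized: 1638 + 220 = 1858.
- Still in follow-up when the trigger is met: 1858 − 1638 = 220.
- Share f = 220/1858 = 11.8%.
- By the 2:2:1:1 allocation: about 73 of 619 in each dupilumab arm (1858/3) and about 37 of 310 in each placebo arm (1858/6).
- If half of the 220 reach Week 52 between trigger and actual lock: 110/1858 = 5.9%.
- If the extra enrolment is 200 to 240 rather than 220: 10.9% to 12.8%.

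**Effect on the responder results.** If the not-yet-due patients are a random share of each arm, a true responder proportion p is reported as p(1 − f). At f = 11.8% the multiplier is 1638/1858 = 0.882. The documents give no responder rates, so the true rates below are assumptions.

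| True rates | Reported at 11.8% | True OR | OR at 11.8% | OR at 5.9% |
|---|---|---|---|---|
| 70% vs 60% | 61.7% vs 52.9% | 1.56 | 1.44 | 1.49 |
| 75% vs 65% | 66.1% vs 57.3% | 1.62 | 1.45 | 1.52 |
| 60% vs 45% | 52.9% vs 39.7% | 1.83 | 1.71 | 1.77 |

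**Approximate unadjusted power at 70% vs 60%**, from a Wald test on the log odds ratio with variance 1/[n₁p₁(1−p₁)] + 1/[n₀p₀(1−p₀)]:
- 619 vs 310, unreached visits as failures: z = 2.57, power 73%.
- 546 vs 273, unreached visits left out: z = 2.85, power 81%.

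Under this rule, adding 220 patients lowers the power of the analysis.

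**Who should be left out.** Suppose a fraction d of the late-randomized patients has already dropped out at lock. The late-randomized group is then L = 220/(1 − d), and the patients whose visit was due number 1858 − L.

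| Assumed d | L | Dropouts in L | Due by lock |
|---|---|---|---|
| 5% | 232 | 12 | 1626 |
| 10% | 244 | 24 | 1614 |
| 15% | 259 | 39 | 1599 |

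Leaving out only the ongoing patients would keep 12 to 39 late-randomized dropouts as failures while their contemporaries disappear from the denominator. The exclusion therefore has to follow the due date and not the patient's status.

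**The case against.** The strongest reply is that missing data has a narrower meaning elsewhere in the SAP. For exacerbations (2.4.4.1.1) it refers to patients who withdraw before Week 52. For FEV1 (2.4.4.1.2) it refers to a skipped scheduled measurement or a withdrawal. Neither covers a visit not yet due, and a sensible programmer might apply a cut-off anyway. But those definitions govern the two primary endpoints, and the responder section sets its own rule without the limitation. A choice that changes reported results should be written down before lock.

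The second reply is low consequence, and much of it stands. The responder analyses supplement the MMRM and do not appear in Table 6. Allocation is random, so the dilution is expected to be similar in all arms. The Week 52 MMRM on the same instruments is unaffected. The addendum will summarize the later data, although that does not correct the results in the final report.

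Third, the size is partly assumed. Both 1638 and 220 are approximate, and if the trigger means the first 1638 patients randomized, 220 is an upper bound: 180 would be 9.7% and 150 would be 8.1%. The wide AQLQ window for Week 52 (Days 309 to 406) could also supply a value for a few ongoing patients from an early-discontinuation visit.

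Finally, any due-date rule discards some observed values, such as those of a patient seen on Day 363 with a cut-off on Day 368. That is a real but small cost.

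**Conclusion.** The concern holds. As written, the rule scores about 220 of 1858 ITT patients (11.8%) as Week 52 non-responders because their visit has not occurred. Responder percentages are multiplied by about 0.88 in every arm, and odds ratios move toward 1, for example from 1.56 to 1.44 at assumed true rates of 70% and 60%. The share falls to 5.9% if half of these patients reach Week 52 before the actual lock.

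The percentage rests on the planned numbers and on a lock close to its trigger. The odds ratios and powers rest on assumed response rates and on not-yet-due patients being spread evenly across arms. Confirmatory conclusions are not at risk. Week 36 could be affected too, but without enrolment dates this cannot be sized.

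**What to change.** Add to SAP 2.4.4.2.1: at each responder time point, the evaluable set is every ITT patient, whether ongoing, completed or discontinued, whose scheduled visit falls on or before the data cut-off. Within that set, a missing value remains a non-response. Patients whose visit was not yet due are left out, whatever their status.

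Count the visit as due at the Table 9 target day plus 5 days, which is Day 365 + 5 = Day 370 for Week 52. The target day runs from randomization, as SAP 2.5.4 already sets: "For the efficacy assessment, the reference date for the derivation of relative days of events or findings will be the randomization day". Five days is the wider of the two visit windows in Protocol 10.1. The general window is ±3 days, and patients who stop treatment are followed "until the end of the study with a +/-5 day window". One allowance then serves everyone.

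A small related clarification belongs in SAP 2.4.4.1.1, which defines observation duration only for patients who reach Visit 18 or withdraw: for patients ongoing at lock, it ends at the cut-off or last contact date.

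The cost is three sentences and one derived flag. The Week 52 responder denominator falls from about 1858 to about 1600 to 1626 under the 5% to 15% dropout assumption. At about 1600 the approximate power at 70% vs 60% is still about 81%. A few patients seen shortly before the cut-off lose an observed value.
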